6. STUDY DESIGN & METHODOLOGY

The study will examine performance and safety as defined in primary and secondary endpoints listed in Section 10. A maximum of up to 20 subjects will be enrolled in the study at up to 2 sites with up to 10 subjects per site. The final number of patients enrolled in the study will be based upon the time duration of the study and the rate of enrollment. In the first two patients, the investigator will stimulate the left phrenic nerve only and conduct CMAP tests and nerve conduction test on both phrenic nerves prior to and at least 3 weeks after the stimulation. These subjects will be examined 30 days' post study, to confirm safety of this method of stimulation of the phrenic nerve before enrolling the remaining patients up to a total of 20 subjects. After successfully demonstrating 30 day follow up on the initial two patients, stimulation will occur in both the left and right phrenic nerves simultaneously for the remainder of the trial. Typically, stimulation will occur once every 3 to 5 breaths and this decision will be left to the discretion of the attending physician. Figure 2 outlines the protocol for placement of the leads.

[figure not shown]

Figure 2. Study Left and Right Phrenic Nerve Pacing

Stimulation will occur for a maximum duration of 48 hours. A number of evaluations will also be conducted to measure the ease of placing and removing the stimulation leads as well as the ability of the lead to accommodate positional changes made by or to the patient.

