6.10 Primary Performance Endpoint: Stimulation Pulse to Capture the Diaphragm

The ability of the stimulation pulse to capture the diaphragm will be assessed using WOB (Work of Breathing Measurements). A logistic regression model with successful capture as the outcome will be used. The model will include repeated measurements within a subject.

6.10.1 Model:

capture = (timepoint) (subject)

where subject is a random effect, and the outcome of capture is yes/no based on whether the stimulation captures the diaphragm.

6.10.2 Hypothesis:

H_0 : The proportion of capture is less than or equal to the performance goal (PG) of 90%.

H_0 : $\hat{p}_1 \leq PG$

H_A : The proportion of capture is greater than the performance goal of 90%.

H_A : $\hat{p}_1 > PG$,

where \hat{p}_1 is the estimated proportion of capture from the logistic model accounting for repeated measurements within a subject.

6.10.3 Sample Size:

The following assumptions were the basis for the sample size calculation for the performance endpoint evaluating stimulation capture of the diaphragm:

- Power: 80%
- 1-sided α : 0.025
- Performance goal: 90%
- Expected success rate: 97.5%

With an anticipated success rate of 97.5% and a performance goal of 90%, 80 observations would yield $\geq 80\%$ power. Note that, for the purposes of sample size calculations, the observations are assumed to be independent. However, the primary analyses will account for within patient correlation, as described below. Increasing the number of observations will increase the statistical power.

6.10.4 Methods:

The proportion of successful capture will be analyzed using a logistic regression model accounting for patient as a random effect. The null hypothesis will be tested comparing the lower bound of the 95% two-sided confidence interval for the estimated percent agreement to the performance goal of 90%. If the lower bound is greater than 90%, the null hypothesis will be rejected and the endpoint will be considered met.

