12. DATA RECORDING AND SUBMISSION REQUIREMENTS

Data

All aspects of the study will maintain patient privacy and be Declaration of Helsinki and General Data Protection Regulation (GDPR) and Data Protection Act 2018 compliant.

All **raw data** will be entered into an Excel or validated spreadsheet format (with patient names excluded) and include all data collected on the patients up to the time the data is frozen including baseline, procedure, and all follow up data available. All data sets provided shall be clean with all queries resolved.

The following are the types of data in the study:

RAW DATA:

1. PEPNS System electronic archive – data recording by the PEPNS system will be electronically archived by Stimdia Medical.
2. Patient history file – this document will confirm patient meets inclusion and exclusion criteria while also documenting all demographic and physiology aspects of the enrolled patient.
3. PEPNS System procedure report – documentation of procedure related information, e.g., sedation, ventilation, stimulation, ultrasound, test article documentation, procedure step checklist and procedure related specifics noted.

CASE REPORT FORMS (CRF):

1. Screening form
2. Index procedure form
3. Adverse event form
4. Patient disposition form
5. Protocol deviation form
6. Device malfunction form
7. Follow up form

SPREADSHEET AND ANALYSES:

1. All data relevant to analysis will be maintained in a validated Excel spreadsheet until the completion of the study. The master spreadsheet will be validated and maintained by Stimdia Medical. All Excel files used for the data analysis must be password protected and only authorized study personnel can have access to the passwords.

Interim analysis and results will be reviewed with the steering committee in a periodic manner.

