An interim analysis of the primary endpoints may be done on the first 10 patients that were stimulated on both phrenic nerves. If they are met the secondary and other remaining analyses will also be performed. If not, the study will continue to enroll patients and all study endpoints and additional analyses will be analyzed when enrollment has been completed. If an interim analysis is done, the significance level used for testing will be 0.0125. At the final analysis (if needed) the significance level used for testing will be 0.0194. These levels were derived using a power cumulative error spending function with the parameter (rho) set to 1.0. This setting produces Pocock type boundaries (i.e. approximately equal spending for the two tests).

If an interim analysis is not done, the final analysis will use a significance level of 0.025 for testing the primary endpoints.

SECONDARY ENDPOINTS

The secondary endpoints are safety related and examine the percentage of patients who receive safe and successful placement of the multipolar lead in the left and right phrenic nerve utilizing ultrasound guidance and the percentage of patients who experience one or more serious device/procedure-related adverse events during the study.

- The percentage of patients who receive safe and successful placement of the multipolar lead in the left and right phrenic nerve utilizing ultrasound guidance will be determined.
- Phrenic nerve stimulation in synchrony with Mechanical Ventilation (MV) breaths will be measured to verify that it occurs with inspiration.
- The percentage of patients who experience one or more serious device/procedure-related adverse events during the study will be reported.

	PEPNS Study Statistical Analysis Plan	Document Number SAP0001	Rev. Level 1
<small>CONFIDENTIAL: THIS DOCUMENT AND ALL INFORMATION CONTAINED HEREIN IS PROPRIETARY TO STIMDIA MEDICAL, INC. AND IS NOT TO BE DISCLOSED WITHOUT THE EXPRESS WRITTEN PERMISSION OF STIMDIA MEDICAL, INC.</small>			

Safe and Successful Lead Placement

The percentage of patients who received safe and successful placement of the multipolar lead on the Left and right phrenic nerve utilizing ultrasound guidance will be evaluated in terms of the mean and standard deviation for preparation, placement, securement, removal and twitching. Twitching includes neck spasms, arm movement, shoulder movement on unwanted visible stimulation. This will be reviewed on a site basis, by neck circumference and BMI.

Adverse Events

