If an interim analysis is performed, the database will be temporarily locked at the time of the interim analysis and the clinical study report will include the date that the data was transferred from the database to the statistician for the interim analysis. It will also specify whether or not the data had been monitored. The secondary end points and other remaining interim analyses will only be performed if the primary endpoints were met. If not, the study will continue to enroll patients and all study endpoints and additional analyses will be analyzed when enrollment has been completed. At the interim analysis the significance level used for testing will be 0.0125 which translates into calculating a 98.75% two-sided confidence interval on the capture rate and comparing the lower bound to 80%. At the final analysis (if needed) the significance level used for testing will be 0.0194 which translates into calculating a 98.06% two-sided confidence interval on the capture rate and comparing the lower bound to 80%. These levels were derived using a power cumulative error spending function with the parameter (rho) set to 1.0. This setting produces Pocock type boundaries (i.e. approximately equal spending for the two tests).

	PEPNS Study Statistical Analysis Plan <small>CONFIDENTIAL: THIS DOCUMENT AND ALL INFORMATION CONTAINED HEREIN IS PROPRIETARY TO STIMDIA MEDICAL, INC. AND IS NOT TO BE DISCLOSED WITHOUT THE EXPRESS WRITTEN PERMISSION OF STIMDIA MEDICAL, INC.</small>	Document Number SAP0001	Rev. Level 1
---	--	-----------------------------------	------------------------

7. MEASURES TO ADJUST FOR MULTIPLICITY, CONFOUNDERS, HETEROGENEITY, ETC.

Since the study cohort was 9 Caucasian men and 1 Caucasian woman and study was very small no heterogeneity, multiplicity or confounder statistical analyses will be run. However, summary data may be presented for the different types of patients (neuro trauma, COPD etc.) to try and see if there were any trends or if therapy was more effective for one of the patient populations since this was one of the study objectives.

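### No final count or cut-off date is fixed, and the 10-patient analysis is not labelled interim or final, so the stated one-sided 0.025 is not secured

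*Protocol*

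**What the plan says.** **Size.** Protocol section 6 sets a maximum of 20 subjects at up to two sites and adds: "The final number of patients enrolled in the study will be based upon the time duration of the study and the rate of enrollment". The study summary and section 10 give up to 18 months only as an estimate or expectation. The sample-size text in section 6.10.3 ("With an anticipated success rate of 97.5% and a performance goal of 90%, 80 observations would yield" at least 80% power) counts observations treated as independent and derives no number of patients. SAP section 2 keeps the first two, left-only patients for safety alone, so at most 20 − 2 = 18 patients count for capture.

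**Looks.** Protocol section 12 states: "Interim analysis and results will be reviewed with the steering committee in a periodic manner". The design is open-label and single-arm, and section 6.6 reserves a right to terminate at any time.

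**Levels.** The protocol sets "1-sided α : 0.025". SAP section 2 allows one optional look at the first 10 bilaterally stimulated patients at 0.0125, then a final analysis at 0.0194, or 0.025 if there is no interim. After an interim that does not succeed: "If not, the study will continue to enroll patients and all study endpoints and additional analyses will be analyzed when enrollment has been completed". SAP section 6 turns the first two levels into 98.75% and 98.06% two-sided intervals, with the lower bound compared to 80%.

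**Cohort.** SAP section 7 (and again section 8) writes: "Since the study cohort was 9 Caucasian men and 1 Caucasian woman". Table 3 in SAP section 2 lists exactly ten patient identifiers, P03 to P12. Nowhere is the analysis of these ten called interim or final.

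**The concern.** A two-look alpha split holds its level only if the timing of the final analysis does not depend on the results. Here the end of enrolment has no fixed count or date. The reviews have no stated number, and capture is not excluded from them. The same ten patients would be judged at 0.0125 if called interim and at 0.025 if called final. Nothing in the text stops a favourable running result from deciding when enrolment is complete, or which label the 10-patient analysis receives. If either happened, a statement that the endpoint was met would not carry the one-sided 0.025 that the plan claims.

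**Working it through.** **Inputs.** One-sided 0.025 (Protocol 6.10.3). Levels 0.0125, 0.0194 and 0.025 and a power spending function with rho = 1 (SAP section 2). Intervals of 98.75% and 98.06% (SAP section 6). Interim at 10 patients and at most 18 in all.

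**Assumptions.** The true capture rate equals the performance goal. Each patient carries equal information, so Z_n = S_n/√n and corr(Z_m, Z_n) = √(m/n). In the result-driven scenarios, enrolment ends at the first success. The documents give no review schedule, so the schedules below are assumed. Scenarios with more than two looks were simulated with several million paths, and two-look figures come from the bivariate normal. Small-sample behaviour of the random-effects logistic model is not included.

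**1. The plan's own levels.** Spent at the interim: 0.025 × (10/20) = 0.0125, as stated. The final level solves P(Z10 ≤ z(0.0125), Z20 ≤ c) = 0.975, which gives 0.0168, not 0.0194. The value 0.0194 is recovered only by adding a binding futility stop (beta spending with rho = 1, 80% power, stop if Z < 0.83). The SAP has no such stop, because enrolment continues when the interim is not met.

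**2. Scale.** The 0.025 level goes with a 95% two-sided interval, so it is one-sided. The two intervals in SAP section 6 give (1 − 0.9875)/2 = 0.00625 and (1 − 0.9806)/2 = 0.0097 one-sided, half of 0.0125 and 0.0194.

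**3. Planned looks at 10 and 18.** Error = 1 − Φ2(z1, z2; ρ), with ρ = √(10/18) = 0.745.
- One-sided 0.0125 and 0.0194: 0.0267
- Two-sided intervals as written: 0.0137

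**4. Enrolment ends on results.**

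| Scenario | One-sided level per look | Error |
|---|---|---|
| Interim declared, intervals as written, end at any of 11–18 | 0.00625, then 0.0097 | 0.024 |
| Interim declared, levels read as one-sided, end at any of 11–18 | 0.0125, then 0.0194 | 0.045 |
| No interim declared, looks at 10 and 18 | 0.025 | 0.041 |
| No interim declared, looks at 12, 15, 18 | 0.025 | 0.044 |
| No interim declared, looks at 10, 14, 18 | 0.025 | 0.047 |
| No interim declared, a look after each patient from 10 to 18 | 0.025 | 0.059 |

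The first row depends on there being no looks before 10 patients. With looks every two patients from 4 to 18 under the same intervals, the error is 0.029.

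**5. Label chosen after seeing 10 patients.** Ten is called final at 0.025 if favourable; otherwise it is called interim and enrolment runs to 18.
- 18 tested at 0.0194 one-sided: 0.036
- 18 tested with the 98.06% interval (0.0097): 0.030

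**The case against.** The sentence on the final number points away from bias, since study duration and accrual rate do not depend on capture. There are bounds, though loose ones: 20 subjects, 10 per site, 4 to 6 months of expected enrolment, about 18 months in all. The steering committee sentence sits in a data-recording section and does not mention capture, testing or stopping. Protocol section 13.5 gives that committee a role in adverse events, patient safety and data integrity. Section 6.6 follows the right to terminate with a review of safety data. SAP section 6 requires a temporary database lock for an interim, and capture is a derived per-breath variable (SAP section 11), not a running tally. The ten listed patients match the planned look at the first ten bilateral patients. The study is a feasibility study with mainly descriptive methods.

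Most of this stands, and it rules out three stronger readings. A reader might infer that enrolment is meant to end on a favourable capture rate; no text says so. A reader might infer that the 10-patient cohort shows the size was chosen from the results; it is equally consistent with the planned interim. A reader might take 0.045 as the size of the problem. That figure needs one-sided levels that conflict with the only interval rule written for that path, and about 0.027 is already there with a fixed final size of 18, because of the 0.0194 level.

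What the objection does not remove is the branch with no declared interim, or with the label left open. The 98.75% and 98.06% intervals give no protection there, because the test then uses 0.025. The SAP says an interim was allowed by the protocol, and the only protocol sentence on interim analysis is the periodic one. Having adopted a formal hypothesis and a spending function, the plan cannot rest on its feasibility status.

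**Conclusion.** The documents do not secure the stated one-sided 0.025, but they do not show that it is exceeded. If the end of enrolment and the label of the 10-patient analysis are independent of the results, this inflation is absent. If an interim is declared and the SAP's intervals are applied as written, with no looks before 10 patients, the error is at most about 0.024 even when enrolment ends on results.

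The exposure is confined to two cases. With no declared interim and enrolment ended on a favourable result, the error is 0.044 to 0.047 with three reviews and 0.059 with one after each patient from 10 to 18, an excess of 0.059 − 0.025 = 0.034 at most among these schedules. With the label chosen after seeing ten patients, it is 0.030 to 0.036, an excess of 0.005 to 0.011. These sizes rest on assumed review schedules and a normal approximation with equal information per patient. The 0.027 for the planned two looks on the one-sided reading is a separate fault in the 0.0194 level. The change is worth making because it is cheap and supplies the condition on which the claimed error rate depends.

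**What to change.** 1. In Protocol section 6 and SAP sections 2 and 6, place the final analysis at 18 bilaterally stimulated patients or a named calendar date, whichever comes first, fixed before any pooled capture, WOB or synchrony rate is computed.
2. State now whether the 10-patient analysis is the interim or the final one, and its level.
3. In Protocol section 12, limit the pooled results shown at periodic steering committee reviews to safety, enrolment and data quality. If further looks at capture are wanted, spend alpha at each. Holding 0.025 over looks at 6, 10, 14 and 18, for example, needs about 0.0097 one-sided per look.
4. Put all levels and intervals on one scale, and recompute the final level for the actual information fraction without a futility stop. With the stated spending function at 10/18, the levels are 0.025 × 10/18 = 0.0139 and then 0.0162 one-sided.
5. If enrolment ends for any other reason, report the capture rate and its interval descriptively.

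The cost is protocol and SAP wording. No extra patients are needed, because the calendar date can close enrolment. The sponsor gives up the freedom to choose the stopping point after seeing performance results.

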6.1 Study Data Analysis and Statistical Methods

In general, summary statistics will include the mean, median, standard deviation, minimum and maximum for continuous measures and the number and frequency for categorical measures. All analyses will be conducted using SAS v9.3 or greater (SAS Institute Inc., Cary, NC, USA). Sample size calculations were conducted using

PASS v14 (PASS 14 Power Analysis and Sample Size Software (2015). NCSS, LLC. Kaysville, Utah, USA, ncss.com/software/pass).

6.2 Inclusion and Exclusion Criteria

Inclusion Criteria: Candidates for this study must meet all of the following inclusion criteria:

1. 18 years or older (Adult).
2. Male or Female.
3. Able and willing to give informed consent or whose legally authorized representative is able and willing to give informed consent.
4. Subject who in the opinion of the admitting consultant/intensivist is likely to be ventilated for > 48 hours from time of recruitment since study treatment will be for up to 48 hours.

Exclusion Criteria: Candidates for this study will be excluded if ANY of the following conditions are present:

1. Subject has a left ventricular ejection fraction (LVEF) < 20%.
2. Subject unlikely to survive 72 hours due to coexisting medical conditions.
3. Subject has an implanted pulse generator or implanted electronic device: Examples: Cardiac pacemaker, Defibrillator, ICD, Watchman, Vagal nerve stimulator, Spinal cord stimulator, Gastric stimulator or Diaphragmatic stimulator.
4. Subject has experienced an Acute Myocardial Infarction (AMI) within 72 hours prior to this screening or subject is on high dose inotropic support or patient is deemed to be in cardiogenic shock.
5. Subject has significant bleeding diathesis, or is at risk of significant haemorrhage, patient is receiving full dose systemic anticoagulation
6. Subject has a known or suspected phrenic nerve paralysis or neuromuscular or inflammatory muscle diseases where the diaphragm itself may not be functional.
7. Subject has an active systemic infection or local infection at or around the insertion site. Subject is neutropenic or has signs of significant immunocompromise.
8. Subject is known or suspected to be pregnant or is lactating.
9. Subject will be unavailable for, or is unwilling to comply with, follow up requirements of the protocol.
10. Subject is currently enrolled or is expected to be enrolled in any other study of an investigational drug or device who has received treatment under that protocol with the investigational product during the 30 days prior to screening.
11. Subject has undergone a surgery or interventional procedure within the neck region aside from placement of an internal jugular (IJ) vein catheter.
12. Subject has been diagnosed and has been treated for neck cancer within the past 5 years.
13. Subject is known to have a demonstrated intra cardiac thrombus on echocardiography.
14. Subject has uncontrolled hyperthyroidism, hypertension.
15. Subject has had any cerebral ischemic event (Stroke or Transient Ischemic Attack TIA) in the 6-month interval preceding the screening date.
16. Subject has degenerative nerve disorders such as amyotrophic laterals sclerosis (ALS).
17. Subject has an elevated hemidiaphragm on chest x-ray.
18. Subject written informed consent not obtained.

6.3 Enrollment

Subjects will be screened to determine eligibility i.e., who meet all inclusion and exclusion criteria. Those subjects that meet the eligibility criteria and who agree to participate in the study will sign an Informed Consent form. Subject is deemed to be enrolled into study when the subject provides written informed consent and agrees to participate in the clinical investigation.

All patients that were attempted to be treated with the PEPNS System (i.e., intent-to-treat patients) but the procedure was aborted will also be followed for 30 days (+7 days) post index procedure for safety (i.e., adverse event collection).

A screening log will be used to determine why patients were screened out of the study.

6.4 Subject Compliance

Subjects will be asked to return to the site for follow up visit at 30 days from the date of treatment to have a chest x-ray and to assess them for adverse events.

6.5 Withdrawal and Discontinuation

Subjects have the right to withdraw from the clinical investigation at any time and for any reason without prejudice to their future medical care by the investigation team or investigation site. Investigator will ask reason for their withdrawal. Investigator will record all information regarding the patient withdrawal and discontinuation.

A subject may be withdrawn from the clinical investigation for the following reasons:

- Subjects may choose to withdraw from the clinical investigation under the terms of the Declaration of Helsinki and General Data Protection Regulation (GDPR) and Data Protection Act 2018 and their consent documentation without having to give a reason;
- Any unanticipated adverse reaction which is, in the opinion of the Investigator, related to the treatment and will endanger the well-being of the patient if treatment is continued;
- Development of any illness(es), infection or condition(s) that might interfere with the protocol;
- Non-compliance with the clinical investigation procedures deemed by the Investigator to be sufficient to cause discontinuation; and
- Any problem deemed by the Investigator to be sufficient to cause discontinuation.

Subject withdrawal and discontinuation will not affect the standard of care the patient receives.

